13	Optical Coherence Tomography & Fundus Autofluorescence.....	18
13.1	OCT Examination Procedure.....	18
13.1	Fundus Autofluorescence Procedure.....	18
14	Ellex Integre NIR Laser.....	19
15	Schedule of Visits.....	20
16	Appendices:.....	22
16.1	References (General).....	22

NEAR INFRARED LIGHT PHOTOBIO-MODULATION TREATMENT FOR DIABETIC
MACULAR OEDEMA (NIRD TRIAL)

INVESTIGATOR SIGNATURE PAGE

I agree to:

Implement and conduct this study diligently and in compliance with the protocol,
good clinical practices and all applicable laws and regulations.

I have read this protocol and I agree to all aspects.

Investigator Printed Name	Signature	Date
---------------------------	-----------	------

Investigator Printed Name	Signature	Date
---------------------------	-----------	------

Investigator Printed Name	Signature	Date
---------------------------	-----------	------

Investigator Printed Name	Signature	Date
---------------------------	-----------	------

Abbreviations of definitions and terms:

AE	Adverse Event
anti-VEGF	anti Vascular Endothelial Growth Factor
BP	Systemic Blood Pressure
BCVA	Best Corrected Visual Acuity
CF	Colour Fundus photography
CRF	Case Report Form
DMO	Diabetic Macula Oedema
eCRF	Electronic Case Report Form
ETDRS	Early Treatment of Diabetic Retinopathy Study
FFA	Fundus Fluorescein Angiography
GCP	Good Clinical Practice
HREC	Human Research Ethics Committee
ICH	International Conference on Harmonization
IOP	Intraocular Pressure
NIR	Near-infra Red
OCT	Optical Coherence Tomography
SAE	Serious Adverse Event
SD-OCT	Spectral Domain Optical Coherence Tomography
TGA	Therapeutic Goods Administration
VA	Visual Acuity
VEGF	Vascular Endothelial Growth Factor

1 Synopsis of Near InfraRed laser for Diabetic Macular Oedema (NIRD) Study

1.1 Background:

Near-infrared light (NIR) at power densities a hundred times lower than conventional thermal treatments have been shown in animal models to promote the healing of injured cells, including blood vessels and neurons in the retina. The Macular Research Group's laboratory research unit has shown that NIR laser reduces vascular leak that occurs after Muller cell ablation in their transgenic model

1.2 Hypothesis:

That treatment with NIR light reduces diabetic macular oedema by exerting a positive beneficial effect at the retinal cellular level

1.3 Trial design:

Patients with diabetic macular oedema in one eye as defined by the eligibility criteria will receive thrice weekly 90 second treatments with NIR laser, supplied by Ellex, for 4 weeks. Twenty one patients will be sequentially allocated into three groups to receive laser doses 25, 100 or 200 mW/cm². The central 1 mm will be shielded so that the fovea will be protected in the event of any unanticipated toxic effect on the retina.

1.3.1 Primary outcome:

- Reduction in central macular thickness measured by optical coherence tomography at the conclusion of treatment and at 8 weeks compared with baseline.

1.3.2 Secondary outcomes:

- LogMAR Best Corrected Visual Acuity (BCVA)
- Time to oedema reduction
- Time to oedema recurrence
- FFA assessment of leak and capillary closure before (at baseline) and after intervention (week 5 and 16)
- Change in retinal sensitivity (dB) as measured by microperimetry from Baseline to Week 1, Week 5, Week 16 and 6 month follow up visit.

1.4 Power calculation:

This study is an exploratory study designed to provide estimates of outcomes for future studies, therefore power calculations have not been applied. Seven patients per group will be sufficient to produce these estimates and will give an indication of the effective dose range

1.5 Significance:

This study will shed light on whether a novel treatment that may complement existing treatments is safe and whether it warrants further investigation in a larger study

2 Research Plan

2.1 Background

Diabetic retinopathy is a common cause of severe loss of vision and the most common cause of blindness in individuals between the ages of 20 and 65 years in developed countries. Swelling of the central retina, or “macular oedema”, is the commonest cause of visual loss in diabetic retinopathy.

Diabetic macular oedema (DMO) has in the past been treated with continuous wave thermal laser photocoagulation to areas of leak in the macula according to established guidelines which take into account the extent of the leak and its proximity to the centre of the macula, the “fovea”. This treatment does not usually improve vision and causes some permanent tissue damage. More recently injections into the eye of drugs such as vascular endothelial growth factor (VEGF) inhibitors or glucocorticoids have become first line treatment for DMO, but these have to be given regularly, they are expensive and they carry a small risk of serious adverse events.

Near-infrared light (NIR) at power densities a hundred times lower than conventional thermal treatments have been shown in animal models to promote the healing of injured cells, including blood vessels and neurons in the retina. Studies claim that NIR treatment augments cellular energy metabolism, enhances mitochondrial function, increases cytochrome C oxidase activity, stimulates antioxidant protective pathways and promotes cell survival.

The major foundation for this work comes from the Macula Research Group’s laboratory studies of the role of metabolic dysfunction in retinal disease.

Mitochondria are an essential component of energy metabolism. They house the cellular machinery for the tricarboxylic acid cycle and oxidative phosphorylation, which together convert pyruvate, produced by the glycolytic pathway, to ATP. Both photoreceptors and “Müller cells”, which are specialized glial cells, contain abundant mitochondria [1]. Müller cells contain mitochondria throughout their length [2]. This enrichment with mitochondria is consistent with the high energy demand of photoreceptors and the high metabolic activity of Müller cells. A potential role of mitochondrial bio-energetic deficits coupled with increased mitochondrial oxidative stress has been observed in neurodegenerative conditions [3].

There is evidence that 670nm Near Infra Red light activates cytochrome c oxidase, a key constituent of the mitochondrial electron transport chain, which subsequently results in increased electron transfer and improved mitochondrial respiration and ATP synthesis [4]. Near Infra Red treatment has recently been reported to attenuate neuronal damage in animal models of retinal degenerations [5,6]. It is believed that Near Infra Red treatment regulates mitochondrial function through increasing mitochondrial membrane potentials for ATP production, thus inhibiting neuronal apoptosis and neuroinflammation and improving glial-neuronal interactions [5, 6-8].

Our preliminary studies on a mouse model of retinal vascular leak caused by selective ablation of Muller cells suggest that Near Infra Red treatment not only protected photoreceptors but also reduced vascular leakage after induced Muller cell disruption. (Figure)

[figure not shown]

Figure. (A-D), Near Infra Red (NIR) treatment did not affect photoreceptors in control (Ctl) mice but protected photoreceptors from injury in Muller cell KO (TG) mice, in which treatment was initiated from immediately after induced Muller cell ablation. (D), peanut-agglutinin (PNA)-stained cone outer segments as shown in (A-C) were quantified by image analysis. (E), evaluation of mitochondrial membrane potentials at the level of photoreceptor inner segments suggested that NIR treatment improved the function of photoreceptor mitochondria. Retinal wholemounts were stained using the JC-1 mitochondrial dye. A shift of the light emission from 525nm (green) toward 590nm (red) indicates increased mitochondrial membrane potentials [9]. (F-J), NIR treatment reduced established retinal vascular leakage. (F, H), fluorescein angiography was performed to confirm vascular lesions in TG mice 3 months after Müller cell ablation. (G), angiogram of an untreated eye in (F). (I), angiogram of the eye in (H) after 9 days of NIR treatment. (J), quantitative analysis of retinal permeability to FITC-dexra indicates that NIR treatment significantly inhibited retinal vascular leakage. N=12~20/group in (D, E and J). NT=Not Treated.

A pilot study completed at the Stokes Veteran Affairs Hospital required patients with non-centre involving diabetic macular oedema to self administer the NIR treatment twice a day for 160 seconds for 2 months achieved a mean reduction in macular thickness of 20%. [10]

Clinical trials of NIR laser treatment for centre involving diabetic macular oedema (see clinicaltrials.gov #NCT00846092 for a study in Wisconsin) have started but no well-conducted study has reported its' results yet

The NIRD Trial described here improves on the Wisconsin Study and the Stokes Study (in which the patients administered the treatment themselves at home using an NIR light emitting diode (LED) [10] through the use of a slit lamp biomicroscope mounted NIR laser generated light source to be administered to the patient in a consulting clinic. This ensures that the amount of treatment is delivered at an accurate predetermined dose only to the part of the retina where it is required.

Review of safety post enrolment of the first cohort in the NIRD study has shown the NIR light to be safe. Results also indicate that a delayed beneficial effect may be present post completion of NIR treatment.

2.2 Objective

This will be a 1 month exploratory study, with outcome measures assessments at 8 weeks and further assessment visit as 12 and 16 weeks, followed by a 6 month safety visit.

The specific aim of the study is to test the following hypothesis:

- That treatment with NIR light reduces diabetic macular oedema

Outcomes

Variables related to the progression or resolution of diabetic macular oedema will be serially examined in the study eye of all patients to determine the effects of NIR treatment. These are:

2.2.1 Primary Outcome Measure at 8 weeks

Reduction in central macular thickness and total macular volume as measured by Spectral Domain Optical Coherence Tomography (OCT)

2.2.2 Secondary Outcome measures at 1month, 8 weeks, 12 weeks and 16 weeks

- Best corrected LogMAR Visual Acuity (VA)
- Time to oedema reduction
- Time to oedema recurrence
- FFA assessment of leak and area of ischemia before and after intervention
- Change in retinal sensitivity (dB) as measured by microperimetry from Baseline to Week 5, 8, Week 16 and 6 month visit.

2.2.3 Safety outcomes will be:

- Any loss of VA
- Any increase in macular thickness as measured by OCT

3 Design

A cohort of 21 patients satisfying the inclusion criteria will be recruited from the outpatient hospital clinic. They will be sequentially allocated into one of three groups. Each group will have seven patients with group 1 enrolment completed first, followed by group 2 and finally, group 3. Each group will be managed identically but will receive a different dose of NIR energy.

Group 1 will be treated with a dose of 25 mW/cm² for 90 seconds (now fully enrolled)

Group 2 will be treated with a dose of 100 mW/cm² for 90 seconds (now fully enrolled)

Group 3 will be treated with a dose of 200 mW/cm² for 90 seconds.

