5.2 Baseline Examination (Screening Visit)

If the patient is willing and has agreed to participate in the study then a complete baseline examination is conducted (does not need to be the same day as the signing of the consent) which includes the following

- a) Visual Acuity. Best corrected visual acuity will be assessed on LogMAR chart
- b) Intraocular Pressure (IOP) measurement
- c) Slit lamp examination for grading of lens opacities
SD OCT: High definition Spectral domain Volume Scan or Macula Cube
Cross Hair scan or HD 5-line raster
- d) Fundus photography and fluorescein angiography. See Section 12 for photography and angiography details.
- e) Fundus autofluorescence. See Section 13.1
- f) Urine pregnancy test (for women of child bearing potential only)
- g) Blood pressure
- h) Assessment of concomitant medications and medical history
- i) Visual function as assessed by Microperimetry

Full baseline assessment will be performed on the Tuesday or Friday on the week immediately prior to starting NIR treatment. If clinics/staff are not available for baseline assessment on Tuesday or Friday, another day in the week immediately prior to starting NIR treatment may be selected, however the remaining treatment and visit schedule must be adhered to according to the protocol.

5.3 Day 1

Once the patient has met all of the eligibility criteria they will return for the Day 1 visit which will occur on the Wednesday the week after screening. The following procedures will occur at this visit:

- a) AE and Conmed history
- b) Microperimetry
- c) Dilation of study eye
- d) Confirmation of eligibility
- e) NIR light treatment

6 NIR Light Treatment

NIR light treatment will commence on the Wednesday of the next week after the baseline visit.

The procedure will be performed whilst the participant is seated at a slit lamp according to the set protocol:

The patient will be seated at the slit lamp laser delivery system and after the eye has been dilated and anaesthetised with topical eye drops a standard fundus contact lens (area centralis) will be placed on the eye through which the posterior pole will be visualised while the treatment is delivered.

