8.1 Primary and Secondary Outcomes

Primary outcome:

- Reduction in high definition Spectral Domain Heidelberg Optical Coherence Tomography (OCT) subfield volume measurements at 8 weeks.

Secondary outcomes at 1 and 2 months:

- LogMAR VA
- Time to fluid reduction
- Time to oedema recurrence
- FFA assessment of leak and capillary closure before (at baseline) and after intervention (Week 5 and 16)
- Change in retinal sensitivity (dB) as measured by microperimetry from Baseline to week 1, week 5, week 8 and Week 16

Safety outcomes will be:

- Any loss of BCVA/VA
- Any increase in any OCT subfield

9 Statistical aspects of the study, safety and reporting

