13.1 Fundus Autofluorescence Procedure

Must be performed prior to fluorescein angiography. Non stereo, Fundus Autofluorescence images should be captured at an angle of 35 degrees with the Heidelberg Spectralis or Zeiss Topcon using the Autofluorescence setting. The images should be captured using the ART mode. Autofluorescence is performed at the baseline, Week 5 and week 16 or early exit visits.

14 Ellex Integre NIR Laser

15 Schedule of Visits

	Screen Baseline Tue ⁱ or Fri ⁱ	Wk1 ^a , 2, 3 & 4 Mon ^a , & Wed	Wk1, 2,3 & 4 Fri	Wk 5 Mon Final Laser Rx	Wk 5 Tue Final Laser on Board Assess ments	Wk 8	Wk 12	Wk 16	6 month Safety Follow Up post last laser	Early Exit
Visit Window						+/- 1wk	+/- 1 wk	+/-1 wk	+/- 2 wk	
Informed consent	X									
Treatment allocation	X									
Con Meds	X		X		X	X	X	X	X	X
Adverse Events & Concomitant Procedures		X	X		X	X	X	X	X	X
Blood pressure	X				X	X		X	X	X
LogMAR BCVA	X				X			X	X	X
LogMar VA	X		X ^c		X	X	X	X	X	X
Microperimetry	X ^h	X ^{g,c,h}			X	X		X	X	
IOP	X				X			X	X	X
Dilated fundal examination	X		X ^c		X	X	X	X	X	X
Cataract grading	X		X ^c		X	X	X	X	X	X
OCT	X		X ^c	X ^b	X	X	X	X	X	X
Fundus Colour Photography	X				X			X	X	X
Autofluorescence	X ^f				X ^f			X ^f	X ^f	X ^f
Fluorescein angiography	X ^e				X			X		X
Urine Pregnancy Test	X ^d									
NIR Laser Treatment		X	X	X ^b						

- a No NIR visit or treatment on Monday of week 1. Wednesday of Week 1 (i.e. 1st NIR treatment visit) must occur the week following the screening visit.
- b Must be done the day prior to the Final assessments visit laser on board visit
- c Must be done prior to laser treatment
- d Required for women of childbearing potential.
- e A suitable angiogram performed within 1 month prior to the baseline visit may be used
- f Must be performed prior to fluorescein angiography
- g Wednesday of Week 1 only
- h At the investigators discretion any participant that did not have microperimetry performed on the study at baseline and week 1, however had standard of care microperimetry at similar timepoints before receiving their first NIR treatment, may be approached for their consent to use this data for study analysis. Participant consent will be obtained by signing an addendum study consent form allowing for the use of this standard of care microperimetry data in the study analysis.

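### Post-laser change in retinal sensitivity is measured from Baseline alone, although a second pre-laser microperimetry test is scheduled in Week 1 and two outcome lists count it as follow-up

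*Protocol*

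**What the plan says.** Protocol section 5.2 puts microperimetry in the baseline examination ("i) Visual function as assessed by Microperimetry"). Section 5.3 puts it again in the Day 1 visit ("b) Microperimetry"), ahead of the NIR treatment in that list. In the section 15 schedule the Week 1 microperimetry entry carries footnote g, "Wednesday of Week 1 only", and footnote c, "Must be done prior to laser treatment". It also carries footnote h, which covers participants without on-study microperimetry at baseline and Week 1. Their standard-of-care tests from similar times before the first treatment may be used, at the investigator's discretion and with addendum consent.

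The outcome is defined three times:

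- Section 1.3.2: "microperimetry from Baseline to Week 1, Week 5, Week 16 and 6 month follow up visit"
- Section 2.2.2: "Change in retinal sensitivity (dB) as measured by microperimetry from Baseline to Week 5, 8, Week 16 and 6 month visit"
- Section 8.1: "Change in retinal sensitivity (dB) as measured by microperimetry from Baseline to week 1, week 5, week 8 and Week 16"

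Section 3 allocates 21 patients sequentially to three dose groups of seven, all of which receive NIR. Section 3.2 states that nobody is masked. Section 1.4 presents the study as one of estimation, without power calculations.

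**The concern.** Both scheduled early tests measure an eye that has had no laser, yet only the first serves as the reference for Weeks 5, 8, 16 and 6 months. Two consequences follow.

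- **Precision.** A difference from one psychophysical test carries the whole retest error of that test. A second measurement of the same untreated state is on the schedule and could reduce it.
- **Bias.** If patients do better the second time because they have learned the test, that gain sits inside every later change from Baseline. With no untreated group and no masking, within-group change cannot tell it from benefit.

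Listing Week 1 beside the post-laser visits in 1.3.2 and 8.1 adds a risk of misreading: a pre-treatment retest difference could be presented as an early treatment outcome.

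**Working it through.** **1. Are both tests before laser?** Yes. Baseline falls on the Tuesday or Friday of the week before treatment, and Day 1 is the following Wednesday. On those days the tests are 8 or 5 days apart. Footnotes c and g place the second before the first laser.

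**2. Is the second test part of the reference?** No. Sections 1.3.2 and 8.1 name Week 1 as a time to which change is measured, so it cannot also be Baseline. Section 2.2.2 does not name Week 1, but the section 15 schedule uses Baseline for the screening column, separate from Week 1. No section averages the two tests or calls the first a practice run.

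**3. Precision.** The protocol gives no standard deviation for microperimetry, so there is no stated figure to reproduce and the results are in units of the retest SD. Let s² be the retest error variance of one test (assumed equal and independent across tests) and τ² the between-patient variance of true change.

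- Reference = one test: Var = s² + s² + τ² = 2s² + τ²
- Reference = mean of two: Var = s² + s²/2 + τ² = 1.5s² + τ²

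| τ²/s² (assumed) | Variance ratio | Variance reduction | Interval narrower by |
|---|---|---|---|
| 0 | 1.5/2 = 0.750 | 25% | 13.4% |
| 0.5 | 2/2.5 = 0.800 | 20% | 10.6% |
| 1 | 2.5/3 = 0.833 | 16.7% | 8.7% |
| 2 | 3.5/4 = 0.875 | 12.5% | 6.5% |
| 4 | 5.5/6 = 0.917 | 8.3% | 4.3% |

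With n = 7 and the t quantile 2.447 (6 df), the 95% half-width at τ² = 0 is 2.447 × √(2/7) = 1.31s with one reference test and 2.447 × √(1.5/7) = 1.13s with the mean. At τ² = 2s² it is 2.447 × √(4/7) = 1.85s against 2.447 × √(3.5/7) = 1.73s.

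**4. Practice.** Suppose scores rise by d from first to second test and then stay level, with no true effect. The apparent change is then:

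| Reference | Bias | d = 0.25s | d = 0.5s | d = 1.0s | Variance |
|---|---|---|---|---|---|
| Baseline test | d | 0.25s | 0.5s | 1.0s | 2s² + τ² |
| Mean of two | d/2 | 0.125s | 0.25s | 0.5s | 1.5s² + τ² |
| Week 1 test | 0 | 0 | 0 | 0 | 2s² + τ² |

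The values of d are assumptions. No single reference achieves both aims: the mean gains precision and halves the bias, while the Week 1 test removes this bias and gains no precision.

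**5. Patients with one pre-laser test.** Let a dose group have a fraction p with only the Baseline test, a fraction q with only the Week 1 test, and the rest with both. If each patient's available tests are averaged, the group's mean bias is p·d + q·0 + (1 − p − q)·d/2 = (d/2)(1 + p − q). Two groups then differ in bias by (d/2) times the difference in (p − q). For illustration, if three of seven in one group had only the Baseline test and all in another had both, the between-dose contrast would be shifted by (d/2)(3/7) = 0.21d. Under one common reference test, a gain shared by all groups cancels.

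**The case against.** Change from Baseline is ordinary endpoint wording, and how repeated pre-treatment values are combined is often left to a statistical analysis plan. That would answer the point if the protocol were silent. It is not: 1.3.2 and 8.1 set Week 1 apart from Baseline, so an analysis plan that used both as reference would depart from them.

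Several objections do stand and limit the point.

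- A reader might infer that nothing in the plan can reveal practice. That is not so. Sections 1.3.2 and 8.1 list Baseline-to-Week 1 change. Subtracting it from a later change gives that later value minus the Week 1 value, which is the Week 1-referenced analysis. The data are planned; they are only labelled and used differently.
- A reader might infer that every patient has two on-study pre-laser tests. Footnote h shows otherwise, and the number with both is not given. The gains in precision apply only to those who have both.
- A reader might attach gains in power. The protocol specifies no power, effect size or SD, and in this document no test for microperimetry, so such figures would be hypothetical.
- Averaging whatever tests exist can itself put unequal practice bias into dose comparisons, as step 5 shows. Groups 1 and 2 were already fully enrolled. If single-test patients cluster in the earlier cohorts, which the protocol does not state, the contrast meant to indicate the effective dose range would be affected.

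**Conclusion.** The point holds in a limited form. The outcome lists leave a scheduled second pre-laser value out of the reference for post-laser change, and two of them present it as follow-up. For patients with both tests, this forgoes at most 25% of the variance of change. In interval width that is about 6.5% to 13% for τ² between 2s² and 0, and less if true change varies more. It assumes equal, independent retest errors.

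A first-to-second-test practice gain, if there is one, passes in full into within-group change from Baseline. The protocol gives no evidence on whether such a gain exists or how large it is, so the exposure is structural and its size is unknown. A gain common to all groups does not affect between-dose contrasts that use a common reference.

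The OCT primary outcome is untouched. For a secondary outcome in an exploratory study this is a worthwhile correction, not a threat to the main conclusion.

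**What to change.** In sections 1.3.2, 2.2.2 and 8.1:

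1. Define the reference for retinal sensitivity change at Weeks 5, 8, 16 and 6 months as the mean of the two pre-laser tests in patients who have both.
2. Take Week 1 out of the treatment outcome times. Report Baseline-to-Week 1 change as pre-treatment retest and practice.
3. Add a sensitivity analysis with the Week 1 pre-laser test alone as reference.
4. Where only one pre-laser test exists, use it, and report the number of such patients in each dose group.
5. Repeat any between-dose comparison with the same single reference test for all patients.

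The cost is wording in three lists, one derived variable and two supplementary tabulations, with no new visit or test. What remains: averaging only halves a first-to-second-test gain, and practice that continues after the second test is not removed by any of these references.

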6.2 Treatment Weeks 2-4

Treatments 2 to 11 will be applied on the Monday, Wednesday and Friday of each subsequent week for 3 weeks.

6.3 Treatment Week 5

On week 5 patients will have their final laser treatment (12) on Monday and will be assessed on the Tuesday.

The investigator can use clinical discretion to determine if the patient would not benefit from receiving further treatment at any time point during the treatment schedule or if any adverse events appear to occur.

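### Dose groups follow one another on completed enrolment alone, and the only safety review reported is of the first cohort, so no review of 100 mW/cm² is stated before 200 mW/cm²

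*Protocol*

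**What the plan says.** Section 1.3 sets the structure: "Twenty one patients will be sequentially allocated into three groups". Section 3 gives the order: "Each group will have seven patients with group 1 enrolment completed first, followed by group 2 and finally, group 3". The three doses and their status follow in the same section:

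- The lowest dose has filled: "Group 1 will be treated with a dose of 25 mW/cm² for 90 seconds (now fully enrolled").
- The middle dose has filled as well: "Group 2 will be treated with a dose of 100 mW/cm² for 90 seconds (now fully enrolled").
- The highest dose carries no enrolment note: "Group 3 will be treated with a dose of 200 mW/cm² for 90 seconds".

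This version of the protocol was therefore written after Group 2 had filled, with only Group 3 still to be recruited.

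On safety, Section 2.1 reports one review: "Review of safety post enrolment of the first cohort in the NIRD study has shown the NIR light to be safe". The sentence after it turns to efficacy and raises a possible late benefit: "Results also indicate that a delayed beneficial effect may be present post completion of NIR treatment". Section 1.5 nevertheless lists the safety of the treatment among the things the study is meant to clarify, and Section 1.3 shields the fovea in case of unforeseen toxicity.

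**The concern.** With ascending doses given to successive groups, a reader expects the protocol to say what must be known about one dose before the next is given. The only ordering condition here is that the previous group has filled. Enrolment is complete before the last patient's treatment begins, so it says nothing by itself about how that dose was tolerated.

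The safety sentence in Section 2.1 compounds this. It rests on the first cohort but speaks of NIR light in general, so it can be read as covering 100 and 200 mW/cm² as well. At stake is whether the step to the highest dose rests on Group 2 data that someone has looked at, and whether ethics committees and patients are told correctly which dose the safety statement concerns. A between-dose condition is protocol content and would not normally be left to an analysis plan.

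**Working it through.** **The plan's own counts.** Three groups of seven give 3 × 7 = 21, as stated. Treatments: 2 in week 1 (Section 6.1), 3 × 3 = 9 in weeks 2 to 4 (Section 6.2) and 1 in week 5 give 12. This agrees with Section 6.3: "On week 5 patients will have their final laser treatment (12) on Monday".

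**What completed enrolment implies for the last Group 2 patient.**
- Allocation is at the screening visit (Section 15).
- Screening is on a Tuesday or Friday and first laser on the Wednesday of the following week (Sections 5.2 and 5.3), so the gap is 8 or 5 days.
- With first laser as day 0, the Monday of week 5 is day 4 × 7 − 2 = 26, and the Tuesday assessment is day 27.
- When the seventh patient is allocated, that patient has had 0 of 12 treatments.

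The screening interval for Group 3 does not rule this out. A last Group 2 patient screened on a Tuesday and a first Group 3 patient screened on the Friday of the same week would both have their first laser on the same Wednesday (8 and 5 days later).

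This is the worst case. The recruitment rate is not given. At an assumed one patient a month, first lasers are about 30 days apart. That exceeds the 26-day course, so the last Group 2 patient would have finished treatment before the first Group 3 laser.

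**Size of the dose step.** Energy per session = irradiance × 90 s; per course = session × 12.

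| Group | mW/cm² | J/cm² per session | J/cm² per course | Ratio to Group 1 |
|---|---|---|---|---|
| 1 | 25 | 2.25 | 27 | 1 |
| 2 | 100 | 9 | 108 | 4 |
| 3 | 200 | 18 | 216 | 8 |

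Group 3 is 200/100 = 2 times the dose for which no review is reported, and 200/25 = 8 times the stated dose of the reviewed cohort. The factor of 8 depends on the 25 mW/cm² in Section 3. Section 10.1 gives an operator-set range of 50 to 500 mW/cm², which excludes 25. Measured from the bottom of that range the ratio would be 200/50 = 4. The protocol does not resolve this.

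**What a review of one group can support.** Section 2.1 gives neither the number reviewed nor the number of events. Assume the most favourable case, all seven reviewed with no events. The one-sided 95% upper bound on the event rate is 1 − 0.05^(1/7) = 0.348, about 35%. The two-sided exact bound is 1 − 0.025^(1/7) = 0.410. Even at the reviewed dose, that falls short of showing the light to be safe.

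**Whether another provision covers the dose step.**
- Section 6.5: VA and OCT each treatment Friday. This monitors individual patients.
- Section 6.3: investigator discretion to stop treatment. This concerns the individual patient.
- Section 6.4: discontinuation on a thickness or acuity criterion. This also concerns the individual patient.
- Section 3.1: monthly staff meetings on methods and problems. No dose decision is assigned to them.
- Section 9.3: a trial-level stop at P = 0.01 for severe adverse events, or on any event against participants' interests. It responds to events and is not tied to a dose step.

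The P = 0.01 criterion has no stated reference rate. Under assumed rates of 1%, 5%, 10% and 20%, the smallest number of events in 7 patients with a binomial tail probability of at most 0.01 is 2, 3, 4 and 5 (tail probabilities 0.0020, 0.0038, 0.0027 and 0.0047). At group size it would seldom act as a check between doses.

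**The case against.** The best defence is that patients are watched closely. VA and OCT are measured before laser every treatment Friday, discontinuation criteria apply throughout, the investigator may stop treatment, the central 1 mm is masked, staff are unmasked and would see problems as they arise, and Section 9.3 includes an open-ended stop for any event against participants' interests. Section 10.1 adds that even the device's highest setting is close to an ordinary aiming beam. All of this stands, and it rules out saying that Group 3 would be unprotected. None of it is a decision point between doses, and the protocol does not offer it as a reason for stepping up without one.

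Several stronger readings are tempting but unsupported:

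- **That no Group 2 review took place.** The protocol neither requires nor reports one, but silence is not evidence that none was done. Nor does Section 3 say that full enrolment is sufficient to open the next group; it gives an order and no further condition.
- **That the protocol warns of late harm.** The sentence in Section 2.1 concerns a possible delayed benefit, and does not say that effects appear only after treatment. If anything, it suggests that some post-treatment data from the first cohort had been seen.
- **That most of Group 2 would be untreated or short of follow-up when Group 3 starts.** That depends on a recruitment rate the protocol does not give.
- **That ascending order was chosen to protect later patients.** The stated aim in Section 1.4 is to indicate the effective dose range.
- **That Section 2.1 states a review of seven patients at 25 mW/cm².** It names neither the number nor the dose. Group 1 is an inference from the enrolment order.

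**Conclusion.** The point holds in a limited form. As written, the plan orders the dose groups by enrolment only and neither requires nor reports a review of Group 2 before Group 3. Its one safety statement is worded more broadly than the cohort behind it and sits uneasily with Section 1.5. The step concerned is a doubling of irradiance from Group 2, and a factor of eight from Group 1 if the Section 3 dose is taken at face value.

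The figure of 0 of 12 treatments is a possible worst case, not an expected value. The conclusion rests on reading the first cohort as Group 1, which the enrolment order supports. It does not depend on any recruitment rate, or on the assumed reference rates used for Section 9.3.

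**What to change.** Reconcile Sections 1.5, 2.1 and 3:

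1. In Section 2.1, confine the safety statement to the cohort, the dose and the number of patients actually reviewed.
2. In Section 3, state which Group 2 safety data already collected under Section 15 (adverse events, VA, OCT) are reviewed and documented before Group 3 treatment starts. The visit and the criteria are for the investigators and the ethics committee to set. If such a review has already been done, record it.
3. Reconcile the 25 mW/cm² dose in Sections 1.3 and 3 with the device range in Section 10.1, so that it is clear what the reviewed cohort received.

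The cost is a protocol amendment, one review and possibly a short delay to Group 3. No additional patients or procedures are needed.
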